2. SAMPLE SIZE AND STATISTICAL POWER CONSIDERATION

Sample Size Considerations (Part A and Part B): The sample size calculation for Part B is based on the secondary endpoint of the mean number of days with any IGISIS individual symptom intensity score ≥ 2 .

Assuming the mean number of days with any IGISIS individual symptom intensity score ≥ 2 is 3.5 and 2.0 for the DMF and ALKS 8700 treatment groups, respectively, a sample size of 500, including 60 randomized subjects per group (120 subjects in total) in Part A and 190 randomized subjects per group (380 subjects in total) in Part B, will provide at least 80% power to detect about a 42% reduction in the number of days with any IGISIS individual symptom intensity score ≥ 2 for the ALKS 8700 treatment group relative to the DMF treatment group, at an alpha level of 0.05 (two-sided) using a negative binomial regression approach. The sample size calculation assumes a standard deviation of 5.9 in the number of days with any IGISIS individual symptom intensity score ≥ 2 relative to exposure days for the DMF treatment group in Part A and Part B.

Assuming the mean number of days with any IGISIS individual symptom intensity score ≥ 2 is 3.5 and 2.0 for the DMF and ALKS 8700 treatment groups, respectively, a sample size of 380 randomized subjects (190 subjects per treatment group) in Part B will provide at least 80% power to detect about a 42% reduction in the number of days with any IGISIS individual symptom intensity score ≥ 2 for the ALKS 8700 treatment group relative to the DMF treatment group, at an alpha level of 0.05 (two-sided) using a negative binomial regression approach. The sample size calculation assumes a standard deviation of 5.9 in the number of days with any IGISIS individual symptom intensity score ≥ 2 relative to exposure days for the DMF treatment group in Part B.

3. DATA ANALYSIS

3.1. General Statistical Methodology

The safety and efficacy endpoints will be summarized by treatment group and overall as described below. In general, summary statistics (n, mean, standard deviation [SD], median, minimum, and maximum for continuous variables, and number and percentage of subjects in each category for categorical variables) will be provided by treatment group and overall. All summary tables will be based on observed data, and missing values will not be imputed unless otherwise indicated. Measurements collected from unscheduled visits or repeated assessments will not be included in the by-visit summary tables or figures, but will be included in the analyses for the potentially clinically significant (PCS) post-baseline values and subject listings. Source data for the summary tables and statistical analyses will be presented as by-subject data listings.

Baseline value is defined as the last non-missing assessment prior to the first dose of study drug.

All statistical tests and confidence intervals (CIs), unless stated otherwise, will be 2-sided and will be set at an alpha level of 0.05.

All the efficacy analyses will be summarized by the planned treatment assignment, and all the safety analyses will be summarized by actual treatment.

The data will be summarized for the following two study periods as appropriate.

- Treatment Period, which is defined as the period between the first dose date after randomization and the last dose date plus 1 day, inclusive.
- Follow-up Period, which is defined as the period between the date of the last dose date plus 2 day and the last study date, inclusive.

3.2. Study Populations

3.2.1. Definitions of Analysis Populations (Analysis Sets)

3.2.1.1. Safety Population

The safety population will include all randomized subjects who receive at least one dose of study drug (ALKS 8700 or DMF).

3.2.1.2. Full Analysis Set (FAS)

The full analysis set (FAS) population will include all subjects who receive at least one dose of study drug and who complete at least one post baseline GI tolerability assessment (GGISIS or IGISIS).

3.2.2. Disposition

Subject disposition will be summarized by treatment group in terms of the following:

- Subjects enrolled in the study
- Subjects in the Safety Population
- Subjects in the FAS population

[REDACTED]

- Subjects who completed the treatment period
- Subjects who completed the study
- Subjects who rolled over to A301 study
- Subjects who discontinued from the study during the treatment period
- Subjects by the reason for early discontinuation

Percentages of disposition will be based on the subjects in the Safety Population. A listing of disposition will be provided for all subjects.

3.2.3. Protocol Deviations

Subjects with major protocol deviations in the following categories will be summarized by treatment group and overall, along with supportive listings for each category as listed below:

- Did not meet the inclusion/exclusion criteria
- Received prohibited medication (as determined by the sponsor medical monitor)
- Lack of adherence with study medication, as defined by subjects taking less than 70% of the protocol-specified amount of study medication
- Randomization or dosing error
- Other major protocol deviation.

3.3. Demographics and Baseline Characteristics

Summary statistics will be provided for all demographic variables and baseline characteristics by treatment group and overall. Demographic data including age, age category (<40, \geq 40 years), gender, race, weight, body mass index, ethnicity and region (US and non-US) will be summarized by treatment group and overall.

Baseline characteristics will be summarized by treatment group, using descriptive statistics. These include years since disease (multiple sclerosis [MS]) onset, years since MS diagnosis, number of MS relapses in the past 12 months, prior MS treatment, [REDACTED].

Baseline magnetic resonance imaging (MRI) parameters (number of gadolinium-enhancing [GdE] lesions, GdE lesion category [0, 1-4, 5-8, and >8], T2 lesion volume and Normalized Brain Volume [NBV]) will also be summarized by treatment group and overall.

Medical history and number of prior disease modifying treatments (DMTs) will be summarized for the safety population using the number of observations and percentage of subjects reporting each category by treatment group and overall.

Demographic, baseline characteristics, medical history and prior MS treatment history listings will be provided for all subjects.

3.4. Prior and Concomitant Medications

Prior medications will be defined as medications taken prior to the first dose of the study medication. Concomitant medications will be defined as medications taken during the period between the first dose date and the last dose date of study drug, inclusive. All medications as documented by the investigator will be coded using the World Health Organization Anatomical Therapeutic Chemical (WHO-ATC) drug dictionary herbal enhanced version (2016, 1st quarter).

Prior and concomitant medications will be summarized by drug class, preferred term, treatment group and overall. Prior DMTs will also be summarized by treatment groups and overall. For the summary tables, if a subject has taken a prior or concomitant medication more than once, the subject will be counted only once for the medication. In addition, a separate listing for concomitant medications used to treat GI related Adverse Events will also be provided.

All reported medications will be presented in a subject data listing.

3.5. Treatment Adherence Rate and Extent of Exposure

The treatment adherence rate will be derived directly using the following formula:

(number of capsules taken) / (number of capsules expected to be taken) * 100.

When a subject discontinues treatment early, the number of capsules that should have been taken is based upon the duration the subject was on treatment.

Study drug adherence will be summarized for each treatment group and overall.

The total number of days the subject is on study drug (time on treatment) will be summarized as a continuous variable and categorized into 1-week intervals. Days on study drug will be calculated as the number of days from date of first dose to date of last dose inclusive.

3.6. GI Tolerability and Efficacy Analyses

3.6.1. General Considerations

GI tolerability assessments will be performed using the FAS Population unless otherwise specified.

All statistical tests will be 2-sided with a type I error rate of 5%, unless otherwise specified. All confidence intervals will be 2-sided 95% confidence intervals. No corrections for multiple comparisons will be applied.

3.6.2. GI Tolerability Assessment

The primary, secondary, and exploratory endpoints are as follows:

Primary Endpoint

- The number of days with any IGISIS individual symptom intensity score ≥ 2 relative to exposure days in Part A and Part B.

Secondary Endpoints

- Number of days with any IGISIS individual symptom intensity score ≥ 2 relative to exposure days in Part B
- Number of days with any IGISIS individual symptom intensity score ≥ 1 relative to exposure days in Part A and Part B
- Number of days with any IGISIS individual symptom intensity score ≥ 3 relative to exposure days in Part A and Part B
- Number of days with a GGISIS symptom intensity score ≥ 1 relative to exposure days in Part A and Part B
- Number of days with a GGISIS symptom intensity score ≥ 2 relative to exposure days in Part A and Part B
- Number of days with a GGISIS symptom intensity score ≥ 3 relative to exposure days in Part A and Part B
- Worst IGISIS individual symptom intensity score by week during the 5 week treatment period in Part A and Part B

Exploratory Endpoints

3.6.2.1. Individual GI Symptom and Impact Scale

The IGISIS is designed to assess the incidence, intensity, onset, duration, and functional impact of 5 individual GI symptoms: nausea, vomiting, upper abdominal pain, lower abdominal pain, and diarrhea. This scale will be subject-completed using e-diaries. These 5 symptoms were included in the IGISIS as they were the most commonly reported GI symptoms in the Tecfidera® Phase 3 placebo-controlled trials. Subjects will be asked to rate the severity of each individual symptom via an 11-point numeric rating scale ranging from 0 (did not have) to 10 (extreme). Subjects will also be asked to indicate the start and stop times of each GI symptom. Additionally, subjects will be asked to indicate how much each symptom has interfered with their ability to accomplish their regular daily activities using a 5-point Likert scale (not at all, slightly, moderately, quite a bit, extremely).

GI tolerability assessment utilizing the IGISIS will focus on intensity scores (11 point numeric severity rating scale) of each individual symptom. If an IGISIS symptom is recorded as ongoing, only the initial intensity score will be collected (i.e., logically skipped item) and the initial intensity score collected at the symptom start will be carried over until symptom end.

Number of days with any IGISIS individual symptom intensity score ≥ 2 relative to exposure days

Number of days with any IGISIS individual symptom intensity score ≥ 2 (event days) is counted among observed diaries. Exposure days are the number of days between a subject's first dose date and last dose date during treatment period, inclusive.

Let $\theta^{(1)}$ and $\theta^{(2)}$ denote the mean number of days with any IGISIS individual symptom intensity scores ≥ 2 , for ALKS 8700 and DMF, respectively. Comparison of GI tolerability will be tested at 5% level of significance in a two-sided test, through the following hypothesis of no treatment effect:

$$H_0: \theta^{(1)} = \theta^{(2)} \quad \text{vs. } H_a: \theta^{(1)} \neq \theta^{(2)}$$

ALKS 8700 will be *claimed superior* to DMF if *the estimated $\theta^{(1)}$ is less than the estimated $\theta^{(2)}$ and p-value is less than 0.05 (in a 2-sided test)*. DMF will be *claimed superior* to ALKS 8700 if *the estimated $\theta^{(2)}$ is less than the estimated $\theta^{(1)}$ and p-value is less than 0.05 (in a 2-sided test)*.

Event days will be analyzed by the negative binomial regression model, including treatment as factor and adjusting for study parts (not included in part B only analyses), region (US and non-US), age and Body Mass Index (BMI). Additional covariates may also be included in the model. The logarithmic transformation of exposure days will be included in the model as the “offset”

parameter. If the data are underdispersed, or if the negative binomial regression model does not converge, a Poisson regression model with the same covariates will be used instead of the negative binomial regression model. Dispersion will be evaluated from the Pearson Chi-square statistic. If the ratio of the Pearson Chi-square statistic to the degrees of freedom is ≤ 1 which indicates no overdispersion, then a Poisson regression model with adjustment for underdispersion will be used. Count distributions in which the number of intervals with zero events is higher than predicted by a Negative binomial or Poisson model may be modeled using a Zero-inflated model.

This method will also be used for the secondary endpoints by setting the GI symptom intensity score cut off as 1 and 3. Empirical cumulative distribution function plot of number of event days by treatment groups will be presented.

Worst IGISIS symptom intensity score by week during the 5 week treatment period

Worst individual IGISIS symptom intensity score is defined as a subject's worst (i.e., highest) symptom intensity score for any symptom out of all completed IGISIS diaries during a given period. Worst IGISIS symptom intensity scores by week during the 5 week treatment period for each subject will be summarized by treatment groups and will be analyzed using an Analysis of covariance (ANCOVA) model. The model will include treatment as factors, and adjusting for study parts, region (US and non-US), age and BMI. Additional covariates may also be included.

Worst IGISIS individual symptom interference level

Worst IGISIS individual symptom interference level is defined as a subject's worst symptom interference level (No symptom < Not at all < Slightly < Moderately < Quite a bit < Extremely) for a particular symptom out of all completed IGISIS diaries during the treatment period. All five GI symptoms (nausea, vomiting, upper abdominal pain, lower abdominal pain and diarrhea) will be reported separately and summarized by treatment groups.

Sensitivity Analysis of IGISIS Endpoints

An evaluable diary is defined as an instance when a subject took study drug prior to completing the diary and completed the diary within the recommended reporting window (2 to 9 hours post-dose). Summary statistics will be presented for IGISIS primary and secondary endpoint by evaluable and non-evaluable diaries. Event days will be analyzed controlling for evaluable and non-evaluable diaries.

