1.2. Summary of the Study Design

This is a randomized, double-blind, multicenter study to evaluate the tolerability of ALKS 8700 and DMF in adult subjects with RRMS. The study was conducted in two parts (Parts A and B). The study design is an adaptive approach where data from Part A was used to modify the GI tolerability endpoint(s) in the study.

Both Parts A and B are identical in study design and include a 5-week, double-blind treatment period with two blinded treatment arms (ALKS 8700 and DMF). Part A is exploratory. The first 120 eligible subjects will be randomized to one of the two treatment groups in Part A (n=60 per group). Once the randomization for Part A is complete, the next 380 eligible subjects will be randomized into one of the two treatment groups in Part B (n=190 per group). Accordingly, subjects 1-120 will be randomized into Part A and subjects 121-500 will be randomized into Part B. Subjects randomized in Part A will not be eligible to participate in Part B.

Following completion of Part A, the sponsor conducted a planned, unblinded analysis of the Part A GI tolerability and safety data. Part B will be ongoing during the analysis of the Part A data. Data from Part A can be used to modify the Part B GI tolerability endpoint(s). Pooled GI tolerability data from Part A and Part B will be analyzed for the primary and secondary endpoints.

All study visits in Parts A and B will be completed on an outpatient basis. The screening period is up to 4 weeks (28 days) including a 1-week lead-in period (prior to randomization) during which subjects will complete two self-administered GI symptom scales daily using e-diaries.

In Part A and Part B, subjects meeting the eligibility criteria will be randomized in a 1:1 ratio to one of two blinded treatment groups as follows:

- Group 1: ALKS 8700 462 mg BID (with 1-week titration)
- Group 2: DMF 240 mg BID (with 1-week titration)

In each part, both ALKS 8700 and DMF will be administered orally BID as blinded study drug; either ALKS 8700 462 mg BID or DMF 240 mg BID with an initial 1-week dose titration period. Subjects will be instructed to take study drug with or without food. However, subjects will be instructed to avoid taking study drug with a high-fat, high-calorie meal. Dosing is described in detail in Protocol Section 9.1.

[figure not shown]

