IGISIS		X ¹³	X ¹⁴	X ¹⁴	X ¹⁴	X ¹⁴	X ¹⁴	X ¹⁴	X ¹⁴	
GGISIS		X ¹³	X ¹⁴	X ¹⁴	X ¹⁴	X ¹⁴	X ¹⁴	X ¹⁴	X ¹⁴	
C-SSRS ¹⁵	X		X ⁴		X				X	X
Randomization			X							
Study Drug Dispensation/Accountability			X	X	X	X	X	X	X	

Abbreviations: C-SSRS=Columbia Suicide Severity Rating Scale; ECG=electrocardiogram; [REDACTED]; ET=early termination; [REDACTED]; GI=gastrointestinal; GGISIS=Global GI Symptom and Impact Scale; IGISS=Individual GI Symptom and Impact Scale; MRI=magnetic resonance imaging; [REDACTED]

² To be conducted within 4 weeks (-28 days) of randomization (Visit 3).

³ To be conducted 1 week before Visit 3 (Week 1/Randomization). The screening period (Visit 1 to Visit 3) may last up to 28 days.

[figure not shown]
A complete physical examination at screening (Visit 1); a brief physical examination at all other scheduled visits.

⁶ Serology testing includes hepatitis B surface antigen, hepatitis C antibody, and human immunodeficiency virus antibody.

⁷ Serum pregnancy at screening (Visit 1); urine pregnancy at randomization (Visit 3).

⁸ Vital sign measurements include temperature, respiratory rate, blood pressure, and heart rate. Vital signs to be collected predose at randomization (Visit 3) and at any time at all other scheduled visits. Blood pressure, respiratory rate, and heart rate will be measured after the subject has been in a seated or supine position for at least 5 minutes.

⁹ ECGs to be collected predose at randomization (Visit 3) and at any time at all other scheduled visits. ECGs will be collected after the subject has been in a supine position for at least 5 minutes.

¹¹ Urinalysis includes urine dipstick, urine microscopy (as applicable), urine beta-2-microglobulin, urine albumin, and urine creatinine.

¹² MRI to be performed at any time between screening (Visit 1) and randomization (Visit 3) provided all other screening criteria have been checked for subject eligibility. MRI must not be performed within 30 days of receiving a course of steroids.

¹³ The IGISIS will be completed twice daily (with at least 6 hours in between each completion) and the GGISIS will be completed once daily using e-diaries during the 1-week lead-in period prior to randomization (Visit 3).

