3.6.2.2. Global GI Symptom and Impact Scale

The GGISIS is a global scale to assess the overall intensity, bothersomeness, and functional impact of GI symptoms experienced during the previous 24 hours. This scale will be subject-completed using e-diaries. Subjects will be asked to rate the intensity and bothersomeness of GI symptoms experienced using an 11-point numeric rating scale. Additionally, subjects will be asked to indicate:

- How much their GI symptoms have interfered with their ability to accomplish their regular daily activities using a 5-point Likert scale (not at all, slightly, moderately, quite a bit, extremely),
- Number of hours of work missed due to GI symptoms,
- Impact of GI symptoms on work productivity using a 5-point Likert scale (not at all, slightly, moderately, quite a bit, extremely).

Number of days with a GGISIS symptom intensity score ≥ 2 relative to exposure days

Number of days with a GGISIS symptom intensity score ≥ 2 (event days) is counted among available diaries. Exposure days are the number of days between a subject's first dose date plus one and last dose date during treatment period, inclusive.

Event days will be analyzed by the negative binomial regression model, using treatment as factors and adjusting for study parts (not included in part B only analyses), region (US and non-US), age and BMI. Additional covariates may also be included in the model. The logarithmic transformation of exposure days will be included in the model as the "offset" parameter. If the data are underdispersed, or if the negative binomial regression model does not converge, a Poisson regression model with the same covariates will be used instead of the negative binomial regression model. Dispersion will be evaluated from the Pearson Chi-square statistic. If the ratio of the Pearson Chi-square statistic to the degrees of freedom is ≤ 1 which indicates no overdispersion, then a Poisson regression model with adjustment for underdispersion will be used. Count distributions in which the number of intervals with zero events is higher than predicted by a Negative binomial or Poisson model may be modeled using a Zero-inflated model.

This method will also be used for the secondary endpoints by setting the GI symptom intensity score cut off as 1 and 3. Empirical cumulative distribution function plot of number of event days by treatment groups will be presented.

Worst GGISIS bothersome score and interference level

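### The worst-IGISIS-score ANCOVA omits the lead-in value of the same score, and three GI models leave their covariate lists open

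*SAP*

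**What the plan says.** Three GI models in the visible text state a covariate list.

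- IGISIS event days (section 3.6.2.1; the primary endpoint and the IGISIS count secondaries): negative binomial regression on treatment, study part when the parts are pooled, "region (US and non-US), age and Body Mass Index (BMI). Additional covariates may also be included in the model". The Poisson fallback takes over the same covariates.
- Weekly worst IGISIS score (section 3.6.2.1; secondary): ANCOVA on treatment, "adjusting for study parts, region (US and non-US), age and BMI. Additional covariates may also be included".
- GGISIS event days (section 3.6.2.2; secondary): negative binomial regression on treatment, part, region, "age and BMI. Additional covariates may also be included in the model".

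No section says which further covariates are meant, how they would be selected, or when.

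The pre-treatment data exist. Section 1.2 describes a 1-week lead-in before randomisation "during which subjects will complete two self-administered GI symptom scales daily using e-diaries". Footnote 13 of Table 1 sets the frequency: IGISIS twice daily, GGISIS once daily. Section 3.1 has a general baseline rule, under which the latest available value before first dosing is the baseline. No visible GI model refers to it.

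On timing, section 1.2 states: "Following completion of Part A, the sponsor conducted a planned, unblinded analysis of the Part A GI tolerability and safety data". It also states: "Pooled GI tolerability data from Part A and Part B will be analyzed for the primary and secondary endpoints".

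**The concern.** There are two separate matters.

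**The ANCOVA lacks the baseline of its own outcome.** An analysis of covariance of a symptom score usually includes the same score measured before treatment, because that is often the strongest predictor available. Here the score is collected for a week before randomisation, but the model uses only part, region, age and BMI. Precision in this secondary endpoint is at stake. Validity is not.

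**The covariate list is open.** Section 3.6.2.1 lets either drug be declared superior on a two-sided p-value below 0.05 from the primary model. While the list is open, that p-value can come from more than one model. The question is sharper than usual because the sponsor has seen Part A outcomes by arm, and those subjects enter the pooled analyses. What is at stake is whether a reader can be sure that the reported model was fixed beforehand.

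**Working it through.** **1. The plan's power figure (section 2).** Inputs: means 3.5 (DMF) and 2.0 (ALKS 8700), SD 5.9, two-sided alpha 0.05, negative binomial regression, 250 per group pooled (60 + 190) and 190 per group in Part B.

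- Dispersion: k = (5.9² - 3.5)/3.5² = 31.31/12.25 = 2.556.
- SE of the log rate ratio: sqrt((1/3.5 + 1/2.0 + 2k)/n) = 0.1536 at n = 250 and 0.1762 at n = 190.
- Effect: |ln(2.0/3.5)| = 0.5596.
- Power: Φ(0.5596/SE - 1.96) = 95.4% pooled and 88.8% in Part B.

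Both meet the stated minimum of 80%. The open list does not alter this.

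**2. Share of data already seen.** 120/500 = 24% of the pooled subjects.

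**3. The models side by side.**

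| Model | Named covariates | Open sentence | Lead-in score |
|---|---|---|---|
| IGISIS event days | part (if pooled), region, age, BMI | yes | not mentioned |
| Weekly worst IGISIS, ANCOVA | part, region, age, BMI | yes | not mentioned |
| GGISIS event days | part (if pooled), region, age, BMI | yes | not mentioned |
| IGISIS sensitivity by diary evaluability | no list of its own | no | not mentioned |

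**4. Gain in the ANCOVA.** If r is the within-arm correlation between the lead-in and on-treatment worst scores, given the other covariates, the variance of the treatment difference falls by the factor 1 - r². The gain is 1/(1-r²):

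- r = 0.2: 1/0.96 = 1.042, about 4%
- r = 0.3: 1/0.91 = 1.099, about 10%
- r = 0.5: 1/0.75 = 1.333, about 33%
- r = 0: no gain, at a cost of one degree of freedom

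The SAP gives no lead-in data, so r is an assumption.

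**5. Would the same covariate help the event-day models?** This was simulated with 250 per arm and the section 2 means and dispersion. Counts were capped at 35 days and the fit was negative binomial maximum likelihood, with 4,000 trials per setting. The covariate was the proportion of completed lead-in days at or above the cut-off. Assumed diary loss: 10% of subjects with no lead-in diary, and 85% of days completed in the rest. Assumed mean lead-in event days: 0.10, 0.35 or 0.70 of 7. The last is a ceiling, because it equals the assumed on-drug DMF rate (3.5/35 × 7 = 0.70).

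- Gamma frailty, correlation 0.3-0.5: sampling-variance ratio 0.985-1.024.
- Gamma frailty, correlation 0.7: 1.005-1.024 at a lead-in mean of 0.10, and 1.042-1.056 at 0.35 and 0.70.
- Smaller repeats under gamma frailty gave 0.99-1.00 and about 0.97-1.04.
- Ratios from the model's own standard errors were 1.010-1.195, so the reported SE overstates the gain.
- Null rejection under gamma frailty: 4.9-6.3% (mean about 5.5%) with the covariate, against 4.5-5.7% (mean about 4.9%) without it.
- Log-normal frailty gave gains of 0-30%. There the unadjusted negative binomial test already rejects 9.2% under the null, so those gains are no sound basis for a recommendation.

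**6. Worst case for the open sentence.** Under no treatment effect, with the same gamma simulation, the better p-value is taken from the models with and without the lead-in score. The rejection rate is 5.0% if the score is not prognostic and 5.8-8.6% at correlation 0.3-0.7. A different set-up, with a continuous lead-in score entered linearly, gave 6.6-10.6% from a base of 5.4-6.2%. Part of that excess is model misfit rather than selection, so the figure depends on the set-up.

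**The case against.** **A plan need not rule out every variable it collects.** Once the open sentence is deleted, an unlisted lead-in score is simply out. This stands for the event-day models, and it is why no lead-in covariate is asked for there. For the ANCOVA, the baseline of the outcome itself is a more specific omission and cheap to repair.

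**The correlation may be weak.** Symptoms before drug need not predict symptoms caused by drug, and many lead-in scores may be zero. This also stands: the gain could be near zero. The cost is then one degree of freedom.

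**The type I figures assume something nobody plans.** They require choosing a model by its p-value on unblinded data from all 500 subjects. Both parts are double-blind, only Part A has been unblinded, and covariates chosen before Part B is unblinded would not give these rates. The Part B-only secondary version of the primary endpoint is also free of the data already seen. All of this stands, and the figures are illustrative only. The visible list of endpoints gives no Part B-only version of the worst-score analysis.

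**Adding a covariate now also follows the Part A unblinding.** True. But the baseline of the same outcome is justified by design rather than by Part A results, and it would be fixed before Part B is unblinded.

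**Other documents may settle the model.** The programming specifications and mock tables are separate and not shown. They may do so, but the SAP's own wording would still permit more.

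A reader might also treat the baseline list in section 3.3, such as "years since MS diagnosis, number of MS relapses in the past 12 months, prior MS treatment", as a set of candidate covariates to search over. The SAP lists these for descriptive summary and proposes none of them for the models.

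**Conclusion.** The point holds in a limited form. The worst-IGISIS-score ANCOVA omits the pre-treatment value of its own outcome although it is collected. Three GI models leave their covariate lists open when 24% of the pooled subjects have already been analysed unblinded.

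The size is modest. The ANCOVA gains about 4%, 10% or 33% in variance at r = 0.2, 0.3 or 0.5, all assumed. The open sentence is a pre-specification weakness; about 5-9% type I error is a worst case that applies only if the model is chosen by result.

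Four stronger readings are tempting and not supported:

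- Omitting the lead-in score does not bias the comparison, because treatment is randomised.
- The primary event-day model is not shown to need a lead-in covariate. Under gamma frailty the gain is near nil (a few per cent at most, at correlation 0.7), and the reported SE becomes slightly too small.
- The SAP does not say that covariates will be picked by result, so type I error is not shown to be inflated.
- Not every GI analysis is affected. The evaluable-diary sensitivity model states no list of its own, and redacted exploratory text cannot be judged.

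**What to change.** Before Part B is unblinded:

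1. In the worst-IGISIS-score ANCOVA, add the worst lead-in IGISIS intensity score as the baseline covariate. Define it as the highest score for any symptom over all completed diaries in the lead-in week, and state that this replaces the section 3.1 last-value rule for this analysis. That rule would otherwise reduce a week of twice-daily entries to one. For subjects with no lead-in diary, use the overall mean across both arms.
2. In the IGISIS event-day model, the ANCOVA and the GGISIS event-day model, delete the sentence allowing further covariates, or confine it to sensitivity analyses labelled as such.
3. Do not require a lead-in covariate in the event-day models.

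The cost is SAP wording, one derived variable from data already collected, and one degree of freedom in the ANCOVA. Closing the lists costs nothing.
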